## Study Methodology

- Study Description

- Design: Randomized controlled trial
- Blinding:
  - Blinded: Data analyst
  - Unblinded: patient, surgeon and anesthesiologist
- Location: Greenville Health System (Patewood Outpatient Hospital and Hillcrest Memorial Hospital)
- Sample size: Sample size estimates are based on the assumptions of a large clinical effect size (>.40) seen at 5 follow up points for the primary outcome measure of pain. Using a fixed effects, special, main and interactions, analysis of variance testing (ANOVA) with a power of 0.80 and an alpha of 0.05, we estimate the need for 86 subjects to achieve statistical significance. To account for loss of follow up, we will target 10% more subjects, thus 95 total participants.
- **Study population**
  - Subjects
    - Recruitment: Consecutive patients undergoing hip arthroscopy will be enrolled in the study
    - Inclusion criteria:
      - Scheduled for outpatient hip arthroscopy by [name]
      - ASA 1-3
      - Ages 18-65
    - Exclusion criteria:
      - Prior surgery on ipsilateral hip
      - ASA 4-6
      - Chronic narcotic usage over 6 months or more than the equivalent of 20mg of morphine per day
      - Current or prior placement of a spinal cord stimulator or intrathecal pump for pain control purposes
      - Allergy to amide local anesthetics
      - Contraindication to regional anesthesia
      - BMI > 40
      - Females who are pregnant or plan to get pregnant during the course of the study

- **Study procedure**

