Patients will be followed in the study surgeon's clinic office per his standard protocol at 2 weeks, 6 weeks, and 3 months post-operatively. Pain scores will be evaluated at this time. Clinical outcome measures and range of motion of the patients' hips will be collected at this time as well. Any adverse reaction from the block will be noted and recorded at all times from the administration of the block and at each clinic follow up. Any signs or symptoms of numbness in the distribution of the fascia iliaca block will be noted.

- Primary endpoint: Quantify the difference in pain in patients who have received a pre-operative FI block versus those receiving no block.
  - Secondary endpoint: Quantify the difference in opioid consumption in patients who have received a pre-operative FI block versus those receiving no block.
  - Tertiary endpoints: Assess differences in episodes of PONV, time in PACU, and proportion of unplanned admissions
- Risks / benefit
  - Risks associated with FI blocks are the following:

Overall the procedure has a very low risk profile. The location of the injection means the risk of intravascular injection, local anaesthetic toxicity, and mechanical nerve damage is extremely low.

Good aseptic technique will minimize the risk of infection. The injection of a large volume of local anaesthetic ensures good spread and reduces the risk of failure. The risk of local anaesthetic toxicity is highest within the first 15 minutes after injection, which makes close monitoring mandatory.
  - The potential benefit is improvement in pain control and opioid consumption in FI patients. The knowledge gained from this study will also be used in future patients with this condition.

- **Statistical Analysis**

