The study incorporates four dedicated follow up points beyond baseline: a) perioperative (1 to 5 days), b) 2 weeks, c) 6 weeks, and d) 3 months. The primary outcome measure (pain) will be analyzed using a fixed effects, special, main and interactions, analysis of variance testing (ANOVA). Opioid consumption will be analyzed using a Pearson chi square or parametric equivalent (depending on final coding). Tertiary end points will be captured using an ANOVA for continuous measures (once tests of normality are completed), or Kruskal Wallis, whereas re-admission rates will be analyzed using a Pearson Chi-square. A p value of 0.05 will be considered statistically significant for all findings. Intention to treat and last value carried forward will be integrated for all analyses.

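### The primary pain ANOVA has no patient term, within-patient covariance or named primary contrast, and the stated 80% power does not belong to a test identifiable from the analysis section

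*Combined protocol and SAP*

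**What the plan says.** All the text is in the combined protocol and SAP.

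- **Analysis (Study Methodology, Statistical Analysis).** The study has "four dedicated follow up points beyond baseline: a) perioperative (1 to 5 days), b) 2 weeks, c) 6 weeks, and d) 3 months". For pain: "The primary outcome measure (pain) will be analyzed using a fixed effects, special, main and interactions, analysis of variance testing (ANOVA"). The section then adds "Intention to treat and last value carried forward will be integrated for all analyses", and applies a 0.05 threshold to every finding. The factors of the ANOVA are not listed.
- **Endpoint (Study Methodology, Study procedure).** "Primary endpoint: Quantify the difference in pain in patients who have received a pre-operative" FI block versus no block. No time point or summary of the scores is given.
- **Sample size (Study Methodology).** The basis is a "large clinical effect size (>.40) seen at 5 follow up points for the primary outcome measure of pain". The method is stated as "Using a fixed effects, special, main and interactions, analysis of variance testing (ANOVA) with a power of 0.80 and an alpha of 0.05", and the result as "we estimate the need for 86 subjects to achieve statistical significance", raised to 95 for losses. Numerator degrees of freedom, number of groups and within-patient correlation are not given.
- **When pain is measured.** The Schedule of Events ticks VAS at baseline, 2 weeks, 6 weeks and 3 months only. The Study procedure section has pain scored in the PACU, with no scale or number of readings, and then at visits in the surgeon's "clinic office per his standard protocol at 2 weeks, 6 weeks, and 3 months post-operatively".

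**The concern.** Scores from one patient are correlated. A fixed-effects ANOVA with a single residual treats every score as an independent observation. An interaction needs a second factor beside arm, and the obvious one in that section is the follow-up point, so the natural literal model is arm, visit and arm-by-visit on pooled scores. In that model the residual is too small for the arm main effect and too large for arm-by-visit.

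If the arm effect decides the trial, an ineffective block could be declared effective on pain well above 5% of the time. If arm-by-visit decides, the test is too strict and loses power for a benefit confined to the early period, which is plausible for a pre-operative block. If each visit is analysed separately, nothing says which one counts. Under every reading, the deciding result could be chosen after the data are seen.

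The sample-size section uses the same ANOVA label, so it should show which test was meant. It does not match the follow-up points in the analysis section.

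**Working it through.** **1. The plan's own figure.** Inputs: alpha 0.05, power 0.80, effect size 0.40 (Sample size). The metric is not named. I read it as Cohen's f because the method is an ANOVA; as Cohen's d, one two-group comparison would need 198 in total. Power comes from the noncentral F distribution with λ = f² × N = 0.16N, numerator df1 and denominator df N − k, where k is the number of groups.

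| Test | df1 | k | N for 80% | Power at N = 86 |
|---|---|---|---|---|
| Arm main effect | 1 | 2-12 | 52 | 0.956 |
| Arm-by-time, 4 follow-ups | 3 | 8 | 73 | 0.873 |
| Arm-by-time, 5 follow-ups | 4 | 10 | 80 | 0.835 |
| df1 = 5, 2 groups entered | 5 | 2 | 86 | 0.802 |
| Arm-by-time, baseline + 5 follow-ups | 5 | 12 | 87 | 0.798 |

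At df1 = 5 the answer is 86 for any k from 2 to 7, and 87 for k from 8 to 12. Then 86 × 1.10 = 94.6, which rounds up to 95. So 86 reproduces with df1 = 5. With two arms and six times, (2 − 1) × (6 − 1) = 5, so arm-by-time over baseline plus five follow-ups is a possible origin. The analysis section has four follow-ups, and over those (2 − 1) × (4 − 1) = 3. The calculation also counts each subject as one independent observation.

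**2. Pooled arm test.** Inputs: four follow-up scores per patient (Statistical Analysis); 43 per arm (86 split 1:1, assumed because no ratio is stated); equal variances (assumed). The documents give no correlation ρ, so a range is used. With R the 4 × 4 within-patient correlation matrix, the pooled model understates the variance of the arm difference by the factor D = (sum of all elements of R)/4:

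- compound symmetry: D = 1 + 3ρ
- AR(1), visits treated as equally spaced: D = 1 + (3ρ + 2ρ² + ρ³)/2

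Type I error = 2 × [1 − Φ(1.96/√D)].

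| ρ | D, compound symmetry | Type I error | D, AR(1) | Type I error |
|---|---|---|---|---|
| 0 | 1.00 | 5.0% | 1.00 | 5.0% |
| 0.1 | 1.30 | 8.6% | 1.16 | 6.9% |
| 0.3 | 1.90 | 15.5% | 1.55 | 11.6% |
| 0.5 | 2.50 | 21.5% | 2.06 | 17.2% |
| 0.7 | 3.10 | 26.6% | 2.71 | 23.4% |

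Simulation of the pooled ANOVA (40,000 null trials per setting) agrees at ρ = 0.3/0.5/0.7: 15.4/21.8/26.5% and 11.3/17.3/23.1%. With a patient-level error term the same arm test holds 4.8-5.1%. Carrying the last value forward does not remove the inflation: with 10% random dropout after the first point and 47 per arm, simulation gives 16.7/22.5/26.7% and 13.0/18.3/24.0%.

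**3. Pooled arm-by-time test.** In the same simulations its type I error is 1.1/0.2/<0.1% (compound symmetry) and 2.5/1.2/0.3% (AR(1)). As an illustration only, take an assumed d = 0.6 at the first point and nothing later. At ρ = 0.5 the pooled test has power 0.39 against 0.81 with unstructured covariance (compound symmetry), or 0.42 against 0.66 (AR(1)).

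**4. Separate tests at four visits.** The chance of at least one p < 0.05 under no effect is 17.3/15.7/13.1% (compound symmetry) and 17.7/16.7/14.2% (AR(1)).

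**5. What 86 can detect at one time point.** Two-sample t test, 43 per arm, 84 df, noncentrality d × √(43/2) = 4.637d. Power is 0.785 at d = 0.6 and reaches 0.80 at d = 0.61.

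**The case against.** The strongest reply is that pooling is nowhere stated. The sample-size section counts subjects, not scores, and the intended analysis may be a repeated-measures model, a patient-level summary or one ANOVA per visit, none of which inflates a single test. That stands: the inflation figures are conditional.

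Second, if arm-by-time was intended, as 5 numerator degrees of freedom would suggest, the pooled test is conservative and false positives are not the problem. That also stands, though the test would then lose power, and nothing in the analysis section says it is the primary test.

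Third, the percentages depend on assumed correlations, equal variances and, for AR(1), equal spacing of visits that are not equally spaced. This is fair. The direction does not depend on the exact value: any positive correlation puts the arm test above 5%, and 0.1 gives 7-9%.

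Fourth, choosing a primary time point is choosing what the trial estimates, and the endpoint text expresses no choice. That limits the remedy: the sponsor should choose.

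The reply does not supply the missing contrast. Even a correct repeated-measures model would leave open which of its tests decides the trial.

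**Conclusion.** The point holds as an unspecified primary test, and should be fixed before analysis. The plan gives no patient term, covariance or primary contrast for repeated pain scores. On the pooled reading, the arm test's type I error is about 16-27% (compound symmetry) or 12-23% (AR(1)) at correlations of 0.3-0.7, and the arm-by-time test is conservative at about 2.5% to below 0.1%. On the separate-visit reading, the chance of at least one false positive is 13-18%. These figures rest on assumed correlations, equal variances and 1:1 allocation.

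The 80% power does not belong to a test identifiable from the analysis section. This rests on reading the effect size as Cohen's f.

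Three stronger conclusions might be inferred and are not supported:

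- That the trial will have a false-positive rate of 16-27%. The documents do not say that scores are pooled or that the arm main effect decides.
- That 86 is too few. At f = 0.40 that number gives power of 0.956 for the arm effect and 0.873 for arm-by-time over four follow-ups, on the sample-size section's own one-observation-per-subject basis.
- That 86 has no possible origin in this design. Arm-by-time over baseline plus five follow-ups has the right degrees of freedom; it conflicts with the four follow-ups in the analysis section.

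**What to change.** 1. **Statistical Analysis.** Replace the fixed-effects ANOVA for pain with a repeated-measures mixed model: arm, time, arm-by-time and baseline VAS, patient as the repeated unit, unstructured covariance, all randomized patients in their assigned arm. Unstructured covariance is preferred because, in simulation under AR(1), the usual within-patient error gave an arm-by-time type I error of 5.4-6.3%.
2. **Primary contrast.** Before the data analyst is unblinded, name one arm difference at one time point, two-sided 0.05. Make other visits and arm-by-time secondary. The sponsor chooses the point. The perioperative point in the Statistical Analysis section is a candidate if a score is actually collected then.
3. **Time points.** Reconcile the Schedule of Events, Sample size, Study procedure and Statistical Analysis sections, so that each pain score has a stated time, scale and place of collection.
4. **Sample size.** Restate the power for the named contrast. With 43 evaluable patients per arm (state the allocation ratio), a single-time-point comparison has 80% power for d of about 0.61 before baseline adjustment. Present this as a detectable difference, not as a planned effect.

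Cost: mainly wording, and no added patients. Any arm main effect will have a larger, correct standard error. If the model replaces last value carried forward for pain, it brings a missing-at-random assumption. If the perioperative point is chosen, one extra VAS per patient may be needed, because none is scheduled between baseline and 2 weeks and the first listed clinic visit is at 2 weeks.

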General anesthesia will be conducted in a standard fashion for all patients. General anesthesia with an endotracheal tube will be induced with IV fentanyl 2 mcg/kg, lidocaine 50mg, propofol 2 mg/kg, and rocuronium 0.6 mg/kg unless another plan is chosen at the discretion of the attending anesthesiologist. Maintenance of anesthesia will be done with O2:air FIO2 50%, isoflurane end-tidal concentration of 0.7-1.4%, and tidal volumes of 7-10 mL/kg with a respiratory rate to maintain an end-tidal carbon dioxide concentration of 30-40 mmHg. Fentanyl will be given in 25-50 mcg increments for HR or BP greater than 20% over baseline. No long acting intra-operative opioids will be administered and only fentanyl will be used. Ephedrine in 5-10 mg increments or neosynephrine in 80-160 mcg increments will be used to treat hypotension at the anesthesiologist's discretion. A minimum of 20mL/kg of IV crystalloid will be administered during the surgery. Ondansetron 4 mg IV will be administered to all patients approximately 30 minutes prior to emergence for PONV prophylaxis.

Post-operatively in the recovery room, hydromorphone will be used as a first line opioid for pain given in 0.2-0.5 mg increments to an initial maximum of 4 mg. Nausea will be treated in a stepwise fashion with promethazine 6.25 mg IV as a first line agent. Second line will be a repeat dose of promethazine 15 minutes after the first dose, followed by diphenhydramine 6.25 mg IV 15 minutes later PRN. Pain scores will be recorded initially upon arrival to the PACU and thereafter until the patient is discharged from the PACU. All episodes of nausea and vomiting will be tallied. Total recovery time in the PACU will be recorded. If a patient is otherwise ready for discharge but remains in the PACU due to a non-medical issue (i.e. bed hold), the time at which the patient could have otherwise been discharged will be

recorded as the PACU end time for the purposes of the study. Any unplanned admissions will be noted. All opioids administered intraoperatively and in the PACU will be recorded and converted to morphine equivalents.

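### Opioid consumption is recorded as an amount, but the plan allows a chi-square test under a coding it never defines; on the recorded total this costs power for a shift in amount and gives no estimate

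*Combined protocol and SAP*

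**What the plan says.** All references are to the combined protocol and SAP.

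- **How it is recorded (Study Methodology, study procedure):** "All opioids administered intraoperatively and in the PACU will be recorded and converted to morphine equivalents". This is a quantity.
- **What the endpoint asks (Study Methodology, secondary endpoint):** "Quantify the difference in opioid consumption in patients who have received a pre-operative FI block versus those receiving no block". The Protocol Summary also makes opioid consumption the secondary endpoint. The Introduction lists it among the primary objectives.
- **How it will be tested (Statistical Analysis):** "Opioid consumption will be analyzed using a Pearson chi square or parametric equivalent (depending on final coding").
- **Other continuous endpoints (same paragraph):** "Tertiary end points will be captured using an ANOVA for continuous measures (once tests of normality are completed), or Kruskal Wallis".
- **What feeds the amount (study procedure):** "General anesthesia with an endotracheal tube will be induced with IV fentanyl 2 mcg/kg", unless the anesthesiologist chooses another plan. For PACU pain relief: "hydromorphone will be used as a first line opioid for pain given in 0.2-0.5 mg increments to an initial maximum of 4 mg".

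The documents do not define the coding, the categories, a cut-point, when the coding is fixed, or which parametric test is meant. They also do not say whether the endpoint is the combined total or the PACU amount alone.

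**The concern.** A Pearson chi-square compares category counts, so an amount has to be cut into categories before it can be used. That discards how much each patient received, and the chi-square p value does not supply the difference in consumption that the endpoint asks for. The wording leaves both the test and the cut open until the variable is coded, which could be after the data are in. The lower-ranked tertiary endpoints get a rule for continuous data, and this higher-ranked one does not. At stake are the power of the secondary comparison and whether the report will contain an effect estimate at all.

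**Working it through.** **The plan's own figure.** No sample size or power is stated for opioids. The 86 is for pain. It reproduces from a fixed-effects ANOVA with f = 0.40, alpha 0.05, power 0.80 and numerator df = 5 (the df is not stated in the plan). The 10% addition gives 86 × 1.10 = 94.6, hence 95. Neither figure bears on the choice of opioid test.

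**Inputs.** From the documents: 95 participants, alpha 0.05. Assumed: 1:1 allocation (48/47), a two-sided test, log-normal amounts with log-SD 0.6, and a block effect that shifts the amount by *d* SD on the log scale. Opioids are recorded on the day of surgery, so all 95 can contribute. The value *d* = 0.615 is roughly what a log-scale t-test detects with 0.80 power at 43/43, the plan's 86. The value *d* = 0.8 corresponds to f = 0.40 for two groups (f = *d*/2), which the plan states for pain only.

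**Why a cut is needed on the total.** Induction fentanyl is standard, so any-versus-none would be nearly constant and could hardly separate the arms.

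**Analytic check at *d* = 0.615.**
- Split midway between the arms: proportions above the cut are Φ(0.3075) = 0.621 and Φ(−0.3075) = 0.379, a difference of 0.242. The standard error is 0.1026 under the null and 0.0996 under the alternative. Power ≈ Φ((0.242 − 1.96 × 0.1026)/0.0996) ≈ 0.66.
- Wilcoxon: power ≈ Φ(*d* × √(3/π) × √(48 × 47/95) − 1.96) = Φ(0.615 × 0.977 × 4.873 − 1.96) ≈ 0.83.

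**Simulation on the combined total** (uncorrected Pearson chi-square, 48/47). The chi-square range reflects which side of the cut the middle value falls on and which arm has 48; independent runs agree to about 0.01.

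| Shift (SD) | Wilcoxon | Median-split chi-square |
|---|---|---|
| 0.4 | 0.47 | 0.27–0.35 |
| 0.5 | 0.65 | 0.40–0.49 |
| 0.615 | 0.82–0.83 | 0.59–0.67 |
| 0.8 | 0.96–0.97 | 0.82–0.88 |

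At 0.615 SD, a tertile chi-square on 2 df reaches 0.66–0.67 and a t-test on the untransformed amount about 0.78. The asymptotic efficiency of a median split against Wilcoxon is (2/π)/(3/π) = 0.667, so it needs about 1.5 times the sample size.

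**PACU amount alone.** Here any-versus-none is a natural split, and the result depends on how the block acts.
- *Shift in need* (assumed normal need, SD 1 mg, 0.615 SD, given in 0.2 or 0.5 mg steps, 4 mg cap). Wilcoxon against any-versus-none is 0.82 v 0.38–0.39 if 5% of controls need none, 0.80 v 0.61–0.62 if 20% do, and 0.70 v 0.66 if 50% do.
- *Change only in whether any is needed* (equal amounts among users, assumed). With any use 65% in the block arm v 90% in controls, chi-square has 0.86 and Wilcoxon 0.57. With 50% v 75%, it is 0.73 v 0.59. The order reverses.

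**The case against.** **The plan does not commit to a chi-square.** It also allows a parametric test, and on the amount that involves no categorising loss. This stands: the power loss is conditional on the chi-square option being used.

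**At a large effect the loss may not matter.** The only effect size in the documents, stated for pain, corresponds to 0.8 SD. There even the median split reaches 0.82–0.88 at 48/47. This also stands, but the documents give no opioid effect size, and at 0.4 to 0.615 SD the loss is about 12 to 24 points.

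**A reader might infer that a chi-square is always the weaker test.** The documents do not support that. They leave open a PACU-only endpoint, and if the block mainly changes whether any opioid is needed, any-versus-none is the stronger test. The power claim is limited to a shift in amount.

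**A reader might also infer that cut-points will be tried until one is significant.** Nothing in the documents proposes several cuts, and the blinding list has "Blinded: Data analyst". Blinding the analyst reduces that risk, so no inflated error rate is claimed. What remains is that the plan does not require the coding to be fixed before the data are seen.

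**Preferring Wilcoxon to a t-test is partly taste.** Agreed. The point is to name one test on the amount with an estimate.

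**Conclusion.** The concern holds in this limited form. The documents record an amount and ask for a quantified difference, but permit a test that needs an undefined cut and returns no estimate. If the chi-square is used on the intraoperative-plus-PACU total and the block shifts the amount, power at 48/47 falls by roughly 8 to 24 points over shifts of 0.4 to 0.8 SD, with the smallest losses at 0.8 SD. The sizes rest on assumed allocation, distribution and effect. Three parts do not rest on them: the test is not specified, the total cannot usefully be split as any-versus-none, and a chi-square p value is not the difference requested. This should be corrected, but it affects a secondary endpoint and not the primary pain analysis.

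**What to change.** Replace the opioid sentence in Statistical Analysis with: *Total opioid consumption (intraoperative plus PACU, in morphine equivalents) will be compared between arms as a continuous variable by the Wilcoxon rank-sum (two-group Kruskal-Wallis) test, with the Hodges-Lehmann difference and 95% CI.* Delete the chi-square and the clause about final coding.

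A prespecified t-test or log-scale analysis with an estimate and CI is equally acceptable (the log scale only if no amounts are zero). If the investigators prefer the PACU amount alone, they should say so before the data are seen and prespecify the any-versus-none comparison beside the test on the amount.

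Cost: one or two sentences and no new data. Downsides: Wilcoxon loses about 5% efficiency against a t-test if amounts are near normal. For a PACU-only amount with many zeros, the Hodges-Lehmann difference may lie near zero and power may be lower than for any-versus-none.

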## Schedule of Events

	BL	Proc	2W	6W	3M
Informed Consent	✓	-	-	-	-
Inclusion/Exclusion	✓	-	-	-	-
Surgical Details	-	✓	-	-	-
Physical Exam-ROM	✓	-	✓	✓	✓
Visual Analogue Scale (VAS)	✓	-	✓	✓	✓
Adverse Event Assessment	-	✓	✓	✓	✓

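### Last value carried forward, required for all analyses, can bias the later-visit pain comparison, and the value to carry for a patient lost before 2 weeks is not defined

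*Combined protocol and SAP*

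**What the plan says.** Under Study Methodology, Statistical Analysis, the plan names four post-baseline points: perioperative (days 1 to 5), 2 weeks, 6 weeks and 3 months. Pain, the primary outcome, is to be analysed by a fixed-effects ANOVA with main effects and interactions. No visit is singled out as primary. The section closes with "Intention to treat and last value carried forward will be integrated for all analyses". The document gives no missing-data assumption, no alternative method, no sensitivity analysis and no definition of the value to be carried.

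Loss is expected. The sample-size paragraph says "To account for loss of follow up, we will target 10% more subjects, thus 95 total participants". It does not split that loss by arm or by visit.

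Three places describe when pain is measured:

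- The Schedule of Events lists the VAS at baseline, 2 weeks, 6 weeks and 3 months. It has none at the procedure and no column for days 1 to 5.
- The study procedure says of the recovery room: "Pain scores will be recorded initially upon arrival to the PACU and thereafter until the patient is discharged from the PACU". For the clinic it gives pain scores "at 2 weeks, 6 weeks, and 3 months post-operatively. Pain scores will be evaluated at this time".
- The Statistical Analysis text adds the day 1 to 5 point, which the Schedule of Events does not collect.

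**The concern.** Carrying a score forward assumes that a patient's pain stays where it was when last measured. After hip arthroscopy it should change over three months, and a nerve block may well lower pain mainly in the first days. A no-block patient lost early would then carry a high acute score to 3 months, and a block patient a lower one. The acute difference leaks into the late comparison even when equal numbers are lost. If loss differs by arm, carrying any score that is higher than true late pain biases the comparison, even a score with the same mean in both arms. Patients know their allocation (Study Methodology, Blinding), so unequal loss is plausible, though nothing shows that it will occur.

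The rule is also incomplete. Two analysts could both follow it and obtain different primary results, because each must decide which score counts as the last one for a patient lost before 2 weeks.

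The concern is bias in repeated pain scores. It is not that standard errors are too small, and carry-forward has little or nothing to act on for outcomes measured once around surgery.

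**Working it through.** **Loss figure in the plan.** 86 × 1.10 = 94.6, rounded to 95, which reproduces the target. The 10% is the only input below that comes from the documents.

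**Assumed inputs** (pain on a 0-10 scale):

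| Mean pain | Block | No block |
|---|---|---|
| Baseline | 5.0 | 5.0 |
| Perioperative | 4.0 | 5.5 |
| 2 weeks | 3.0 | 3.5 |
| 6 weeks | 2.5 | 2.5 |
| 3 months | 2.0 | 2.0 |

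The true 3-month difference is 0. Loss is unrelated to pain.

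**Formula.** False 3-month difference, block minus no block = (loss in block × block gap) − (loss in no block × no-block gap), where the gap is the mean carried score minus 2.0. A negative value favours block.

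**Gaps by case**

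1. All loss before 2 weeks, perioperative score carried: 4.0 − 2.0 = 2.0 and 5.5 − 2.0 = 3.5. This is the worst case on timing.
2. Loss spread evenly over the three intervals: (2.0 + 1.0 + 0.5)/3 = 1.167 and (3.5 + 1.5 + 0.5)/3 = 1.833.
3. All loss before 2 weeks, baseline carried: 5.0 − 2.0 = 3.0 in both arms.

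**Results**

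| Loss, block / no block | Case 1 | Case 2 | Case 3 |
|---|---|---|---|
| 10% / 10% | 0.200 − 0.350 = −0.150 | 0.117 − 0.183 = −0.067 | 0.30 − 0.30 = 0 |
| 5% / 15% | 0.100 − 0.525 = −0.425 | 0.058 − 0.275 = −0.217 | 0.15 − 0.45 = −0.30 |
| 15% / 5% | 0.300 − 0.175 = +0.125 | 0.175 − 0.092 = +0.083 | 0.45 − 0.15 = +0.30 |

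With 47 per arm, 5%/15% means about 2 and 7 patients (47 × 0.05 = 2.35; 47 × 0.15 = 7.05). Overall loss is the same 10%.

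**Simulation.** 8,000 runs per scenario, 47 per arm, assumed SD 2 and correlation 0.5, two-sided t-test at 3 months. Rejection rates when the true 3-month difference is 0:

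| Loss, block / no block | Case 1 | Case 2 | Case 3 |
|---|---|---|---|
| 10% / 10% | 6.4% | 5.2% | 5.1% |
| 5% / 15% | 15.0% | 8.0% | 9.9% |
| 15% / 5% | 5.5% | 5.1% | 9.9% |

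Repeat runs agreed to within about one percentage point. The standard errors were sound: in case 1 at 10%/10% the mean standard error was 0.447 against a sampling SD of 0.452. Maximum likelihood on the observed scores, with baseline as one of the outcomes, had absolute bias of at most 0.006 in all nine scenarios. Its sampling SD was 0.425 to 0.433, against 0.420 to 0.454 for carry-forward.

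**Effect of the undefined carried value.** In a second assumed set, the 3-month mean is 2 in both arms, SD 2, correlation 0.4, with 48 and 47 patients. The carried score is either baseline (5 in both arms) or an early post-operative score (4 block, 6 no block).

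| Loss, block / no block | Baseline carried: bias, rejection | Early score carried: bias, rejection |
|---|---|---|
| 10% / 10% | 0.0, 5.0% | −0.2, 7.0% |
| 5% / 15% | −0.3, 9.8% | −0.5, 18.1% |
| 15% / 5% | +0.3, 10.1% | +0.1, 5.7% |
| 20% / 20% | 0.0, 5.1% | −0.4, 12.5% |

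The choice of carried score alone moves the estimate by 0.2 to 0.4 points at the same loss.

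**The case against.** **The planned test is different.** The plan specifies one ANOVA over the visits, not a 3-month t-test. In the first assumed set the arms truly differ early, so a significant ANOVA would not be a false positive. This stands as a limit on the rejection rates, which describe only a separate 3-month comparison. It does not remove the bias. The true arm differences at the four post-operative points are −1.5, −0.5, 0 and 0, averaging −0.50. Under case 1 at 10%/10% they become −1.5, −0.6, −0.15 and −0.15, averaging −0.60. At 5%/15% they become −1.5, −0.75, −0.375 and −0.425, averaging about −0.76. Carry-forward also narrows the spread of arm differences across visits (from 1.5 to 1.35 at 10%/10%), which would tend to weaken the interaction.

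**The larger figures need unfavourable assumptions.** The 15% requires threefold unequal loss, all of it before 2 weeks, and the perioperative score carried. This is correct. At balanced 10% loss the effect is small, and with equal loss and parallel pain courses it is zero.

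**Read literally, the last value is the most recent score.** Anyone operated on should have a recovery-room score later than baseline. This narrows the ambiguity without closing it. The Schedule of Events lists no VAS at the procedure, so those scores may not belong to the series. Randomisation takes place at clinic enrolment, so a patient lost before surgery has only a baseline score. Several recovery-room scores exist per patient, and the last may follow titrated opioid.

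**A smaller repair might do.** One could define the carried score, add a likelihood-based or imputation analysis, and keep carry-forward as a sensitivity analysis. That would answer part of the point, but it offers no reason to leave the biased rule in the main analysis. It is also fair that the 86 was derived for the ANOVA and that no power has been computed for a replacement model.

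**Conclusion.** The concern holds. The plan applies carry-forward to a primary outcome that should change over time, offers nothing to set against it, and leaves the carried score open for patients lost before 2 weeks. The last part follows from the text alone and needs no assumed numbers.

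The size and direction of the bias depend on loss by arm, the timing of loss and the pain course, none of which the documents give. Under the first assumed set the false 3-month difference runs from 0.43 points favouring block to 0.30 against it. It is at most 0.15 points when the planned loss is balanced. The right statement is that carry-forward can bias the late comparison, not that it will. The change should be made before the analysis, but the point does not by itself undermine the trial.

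**What to change.** In Statistical Analysis:

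- Delete carry-forward and keep intention to treat.
- Analyse pain by randomised arm with a likelihood-based mixed model for repeated measures on all observed scores, valid under missing at random. Include arm, visit and arm-by-visit with unstructured covariance. Model baseline as one of the outcomes so that patients with no post-operative score stay in; they add little information on the arm difference.
- State which score is the perioperative value, and reconcile the Schedule of Events, the recovery-room text and the day 1 to 5 point.
- Report loss by arm and visit.
- Add one multiple-imputation sensitivity analysis that shifts imputed block-arm scores by 0, 1 and 2 points (an assumed range on an assumed 0-10 VAS).
- For opioid total, PACU time, PONV and admission, use no carry-forward. Analyse as observed by randomised arm and report the number missing.

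When rewriting, also name the contrast that decides the primary question and align the model named in the sample-size paragraph.

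The cost is SAP wording and slightly more analysis work. No new data are needed and no change to the 95 is proposed. In the simulation the model's precision at 3 months was about the same as that of carry-forward. The text should be fixed before the analyst sees results by arm.
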